## **8.10 Secondary Endpoints and associated hypotheses**

No hypothesis testing is performed for the secondary endpoints. There is no multiplicity adjusted.

Secondary effectiveness endpoints will be analyzed on the FAS and run-in set unless otherwise specified.

### **8.10.1 Technical Success Rate**

Analyses will be performed at target tumor level.

Technical Success Rate is defined as the percentage of tumors that achieve A0 or A1 ablation (i.e., the ablation zone covers the tumor completely and has a surrounding minimal margin) based on the lung CT immediately following the initial ablation procedure. Technical Success Rate will be assessed by both IRC and investigators.

The number and percentage of tumors achieving Technical Success assessed by the IRC and investigator will be analyzed, respectively, and the corresponding 95% CI based on the Normal Approximation to Binomial Distribution (Z-test that uses S(Phat) to estimate the standard deviation) or Clopper-Pearson method (if the proportion is greater than 90%).

Listings, including IRC assessment and PI assessment, will be provided.

### **8.10.2 A0 Ablation Rate**

Analyses will be performed at target tumor level.

A0 Ablation Rate is defined as the percentage of tumors that achieve A0 ablation (i.e., the ablation zone covers the tumor completely and has a minimal margin of at least 5mm for secondary lung tumors and at least 10mm for primary lung tumors) based on the lung CT immediately following the initial ablation procedure. A0 Ablation Rate assessed by IRC or investigators will be summarized, respectively, and the corresponding 95% CI based on the Normal Approximation to Binomial Distribution (Z-test that uses S(Phat) to estimate the standard deviation) or Clopper-Pearson method (if the proportion is greater than 90%).

### **8.10.3 Re-ablation Technical Success Rate**

Analyses on those with re-ablation will be performed at target tumor level.

Re-ablation Technical Success Rate is defined as the percentage of tumors that achieve Technical Success based on the lung CT immediately following the repeat ablation with the study device during the study. Re-ablation Technical Success will be assessed by both the IRC and investigators. Re-ablation Technical Success Rate assessed by IRC or investigators will be summarized, respectively, and the corresponding 95% CI based on the Normal Approximation to Binomial Distribution (Z-test that uses S(Phat) to estimate the standard deviation) or Clopper-Pearson method (if the proportion is greater than 90%).

Listings, including IRC assessment and PI assessment, will be provided.

### **8.10.4 Local Tumor Progression**

Analyses will be performed at target tumor level.

The number and proportion of target tumors with local tumor progression will be summarized and the corresponding 95% CI based on the Normal Approximation to Binomial Distribution (Z-test that uses S(Phat) to estimate the standard deviation) or Clopper-Pearson method (if the proportion is greater than 90%).

On the run-in set, only the number and percentage target tumors with local tumor progression will be provided.

The following analysis will be performed on the FAS and at target tumor level.

Local tumor progression rates of any original-ablated tumor(s) at 3, 6, 9, and 12 months will be estimated by the Kaplan-Meier method and their corresponding 95% CIs will be calculated using Greenwood's formula for estimating the variance and log-log transformation with back transformation to CIs on the untransformed scale.

Time to local tumor progression duration (determined by the CT imaging date, including unscheduled visits) will be summarized descriptively using the Kaplan-Meier method for median and quartiles with 95% CIs estimated using the Brookmeyer-Crowley method. The

censoring rule is described as below and frequency of tumors (n, %) experiencing local progression events and the censored reasons will be provided.

For original-ablated tumor(s) without LTP during the study follow-up period, the tumors will be censored at the date of last local tumor assessment.

Listings, including target tumor ID, ablation date, IRC assessment and PI assessment, local tumor progression date, duration (weeks) will be provided.

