4.2. Application of Investigational Product

Brace et al²⁶ first reported the clinical efficacy and safety of investigational product Certus Microwave Ablation System and accessories for lung cancer ablation. Five patients received percutaneous microwave ablation to treat lung cancer and were followed up for 18 months, all ablation procedures were technically successful without local tumor recurrence or serious complications during follow up.

Kurilova et al²⁷ reported the results of percutaneous microwave ablation for the treatment of 0.3-3.2 cm colorectal cancer lung metastases, the median follow-up time was 25.6 months. Among the 90 lung cancer lesions of a total of 50 patients, Certus Microwave Ablation System and accessories was used in 91% of the lesions. The total Technical Success rate was 99%, the Technical Efficacy was 90% for the first treatment and 92% for the second treatment. During the follow-up period, 10%

of the tumors showed local progression, and the median OS was 58.6 months. The incidence of complications requiring intervention in hospital was 10%.

4.3. Product Registration Profile and Reason for Conducting the Registration Clinical Trial in China

The Certus Microwave Ablation System and Accessories have been cleared by the United States (US, country of origin) Food and Drug Administration (FDA) and has been in clinical use since 2011 in the United States. The most common applications by clinicians have been the ablation of liver, lung, and kidney lesions. In addition, it is also used for the ablation of bone tumors.

Certus Microwave Ablation System and accessories have been approved by National Medical Products Administration (NMPA) and can be used for ablation of liver tumors from January 8th, 2020. However, there is no data on the use of this device for lung tissue ablation in the Chinese population. Therefore, this clinical study aims to support the registration of this device for lung cancer ablation indication in China.

5. FEATURES, STRUCTURAL COMPOSITION, OPERATION PRINCIPLE, MECHANISM OF ACTION, AND STUDY POPULATION

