10. FEASIBILITY ANALYSIS

10.1. Analysis on the Possibility of Success

Pre-clinical and clinical data has shown that MW ablation is safe and effective in small lung tumors with low complication rates, high rates of Technical Success, low rates of Local Tumor Progression. In terms of clinical results of thermal ablation therapy for primary lung cancer, the OS of thermal ablation therapy is approximately 86% at 1 year and 69% at 2 years^{15,16}. Regarding the use of thermal ablation for the treatment of secondary lung cancer, a prospective observational study found that for small secondary lung cancers, reuse of thermal ablation resulted in a survival benefit similar to surgical resection. This includes 566 patients with a total of 1037 secondary lung tumors. By controlling the lung tumors with repeated thermal ablation during the follow-up period, the OS of this population is 62 months, the 5-year survival rate is 51.5%, and the 4-year local treatment effectiveness is 89%²¹.

The Certus Microwave Ablation System and Accessories have been cleared by the United States (US) Food and Drug Administration (FDA) and has been in clinical use since 2011 in the United States. The growing popularity of the Certus Microwave Ablation System in lung cancer ablation therapy result from its low risks of complications and high effectiveness in ablating lesions of the lung. The published clinical data on Certus lung ablation is limited. But from previous data, there is a high likelihood of meeting the protocol Technical Efficacy goal and previous major complications rate was low, which is unlikely to cause discontinuing of the study due to safety concerns.

The study device is provided free of charge and does not increase the burden on subjects, so the recruiting and screening of subjects will not be fairly difficult. Patients need to return to their study site for continued follow-up, a total of 4 times, lasting for 1 year, which is in line with the frequency of clinical routine visits after lung cancer ablation. So it will not be too difficult to obtain the results of the visits required for the study.

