## **8.15 Subgroup Analysis**

Analyses will be done on the FAS for exploratory purpose appropriately.

Descriptive subgroup analyses of the following effectiveness endpoints at the tumor level, including but not limited to Technical Efficacy Rate, and technical success rate.

The number, percentage, and its two-sided 95% Clopper-Pearson CI will be provided.

The following subgroup variables will be considered:

- Tumor type: Stage IA1 NSCLC, Stage IA2 NSCLC, Oligometastatic lung tumor, Other
- Sites

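### The exact interval replaces the Wald interval only above 90%, which is the wrong end for the crude Local Tumor Progression proportion and leaves small-sample re-ablation rates open to upper limits above 100%

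*SAP*

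**What the plan says.** SAP 8.10.4 first treats LTP as a simple proportion: "The number and proportion of target tumors with local tumor progression will be summarized", with a 95% interval from the normal approximation, specified as "Z-test that uses S(Phat) to estimate the standard deviation) or Clopper-Pearson method (if the proportion is greater than 90" percent). SAP 8.10.3 applies the same rule to Re-ablation Technical Success, where the denominator is only the tumors that were re-ablated. Neither section has a matching switch for low proportions, a minimum count, or a truncation rule.

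SAP 8.10.4 also plans a second analysis: "Local tumor progression rates of any original-ablated tumor(s) at 3, 6, 9, and 12 months will be estimated by the Kaplan-Meier method", with Greenwood variance and log-log intervals.

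On the likely size of LTP, Protocol 10.1 speaks of "high rates of Technical Success, low rates of Local Tumor Progression". Protocol 4.2 gives one figure, from a published series in which this system treated 91% of the lesions: 10% "of the tumors showed local progression, and the median OS was 58.6 months", where "the median follow-up time was 25.6 months".

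SAP 8.10 states "No hypothesis testing is performed for the secondary endpoints". For subgroups, SAP 8.15 uses the exact interval with no threshold: "The number, percentage, and its two-sided 95% Clopper-Pearson CI will be provided".

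**The concern.** The Wald interval is unreliable when a proportion is near 0 or near 1, or when the denominator is small. A switch to an exact interval above 90% guards one of these situations: a success rate close to 100%. LTP is an unwanted outcome, and a working device puts it near 0. The switch would operate only if more than nine tumors in ten progressed.

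Re-ablation Technical Success is a success rate, so the switch faces the right way. But few tumors may contribute, because Protocol 7.2.3 allows study-device re-ablation only for local progression, residual tumor or insufficient margin. With few tumors, an observed rate at or somewhat below 90% keeps the Wald interval where it works badly.

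At stake is the accuracy of the reported limits. An upper limit on progression that is too low errs in the device's favor, and negative limits or limits above 100% could appear in the report tables.

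**Working it through.** **Scale of the denominator.** The plan states no numerical result for these intervals. Its nearest figure is the sample size, which reproduces: n = [(1.960×√(0.8×0.2) + 0.842×√(0.9×0.1)) / 0.10]² = 107.4, so 108 evaluable, and 108/0.90 = 120 enrolled. Subjects with oligometastatic tumors can contribute up to three, so I assume tumor totals of 108 to 200.

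**Inputs.**
- Rule (SAP 8.10.3, 8.10.4): Clopper-Pearson if x/n > 0.90; otherwise p̂ ± 1.96×√(p̂(1−p̂)/n).
- LTP: 10% at a median of 25.6 months (Protocol 4.2). This trial stops at 12 months, so below 10% is a fair inference. I use 5–10%, and 2–3% as a more favorable assumption.
- Re-ablation: 5 to 15 tumors and true success of 0.80–0.99, all assumed. The documents give no re-ablation count or rate.
- Tumors are treated as independent.

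**Single intervals, LTP with 150 tumors.**

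| Events | SAP rule | Clopper-Pearson |
|---|---|---|
| 0 | 0% to 0% | 0% to 2.4% |
| 3 | −0.2% to 4.2% | 0.4% to 5.7% |
| 8 | 1.7% to 8.9% | 2.3% to 10.2% |
| 15 | 5.2% to 14.8% | 5.7% to 16.0% |

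For 3 events: p̂ = 0.02 and 1.96×√(0.02×0.98/150) = 0.0224, which gives −0.0024 to 0.0424. The lower limit is negative for 1, 2 and 3 events at each total checked (50, 90, 108, 120, 150, 200).

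**How often so few events occur** (binomial, 120 tumors).

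| True LTP | 0–3 events | Exactly 0 events |
|---|---|---|
| 2% | 78% | 9% |
| 3% | 51% | 2.6% |
| 5% | 14% | 0.2% |
| 8% | 1% | under 0.01% |
| 10% | 0.2% | under 0.01% |

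**Coverage.** Exact binomial sums over every tumor total from 108 to 200.

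| True LTP | Method | Coverage, range (mean) | Upper limit below truth, range (mean) |
|---|---|---|---|
| 5–10% | SAP rule | 88–95.5% (93%) | 3.5–11.3% (5.9%) |
| 2–3% | SAP rule | 79.5–95% (89%) | 5–20% (10%) |
| Both ranges | Clopper-Pearson | at least 95% | at most 2.5% |

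The fault is therefore not confined to 0–3 events. At 5–10% the limits look plausible, but the upper one is too low about 5.9/2.5 = 2.4 times as often as stated.

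**Kaplan-Meier with no events.** The estimated progression-free proportion stays at 1 and the Greenwood variance is 0. The log-log transform log(−log 1) is undefined, so no interval exists. The crude 0% to 0% would then be the only LTP rate interval.

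**Re-ablation.**

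| Result | SAP rule | Clopper-Pearson |
|---|---|---|
| 4/5 | 45% to 115% | 28% to 99.5% |
| 7/8 | 65% to 110% | 47% to 99.7% |
| 9/10 | 71% to 109% | 55% to 99.7% |

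For every denominator from 2 to 30, at least one result at or below 90% has an upper limit above 100% (27/30 gives 100.7%); from 31 to 50 none does. With 5, 8, 10 or 15 tumors, the chance of a limit above 100% is 40–63% at true success of 0.80–0.90, 17–39% at 0.95, and 1–10% at 0.99. Coverage at 0.80–0.90 is 97% or more; it falls short (84–94%) only at some true rates of 0.50–0.70.

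**The case against.** The strongest reply is that the crude LTP interval hardly matters. Protocol 8.1 plans LTP by Kaplan-Meier alone; the crude interval is a SAP addition beside rates at four time points with log-log intervals. Nothing is tested on it. The worst figures also need LTP rates that the documents do not state: at 5–10% mean coverage is 93%, and at 8 or 15 events in 150 the limits differ from the exact ones by only 0.5 to 1.3 points. The zero-event case is rare unless LTP is very low.

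On re-ablation, the count is unknown. The only Technical Success figure in the documents is 99% (Protocol 4.2, overall rather than re-ablation); at that rate most results exceed 90% and the exact method applies. Coverage at 0.80–0.90 is not short, so a limit above 100% is largely a matter of presentation, although lower limits do differ (45% against 28% for 4/5). Subjects may also have several tumors, so Clopper-Pearson is not guaranteed nominal coverage either.

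All of this stands as a limit on weight. None of it removes the fault. The SAP commits to the crude proportion with its own 95% interval, so a poor interval would stand beside a sound one, or stand alone if there are no events. Truncating at 0 or 100% is not specified, and would repair neither the zero width nor the low upper limit.

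**Conclusion.** The concern holds. The 90% switch cannot protect a proportion expected near or below 10%, so the SAP as written gives the crude LTP rate an interval whose upper limit is too low 5.9% of the time on average (nominal 2.5%) at true rates of 5–10%. The average rises to about 10% at 2–3%. Impossible or zero-width limits require 0 to 3 LTP events, or a re-ablation result at or below 90% on at most 30 tumors.

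These sizes rest on independent tumors, tumor totals of 108–200, and assumed LTP and re-ablation rates; only the 10% LTP figure comes from the documents.

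The consequence is confined to the descriptive precision of two secondary endpoints. The primary criterion and the registration decision are untouched, the Kaplan-Meier LTP intervals are sound when events occur, and no failure is claimed for Technical Success or the A0 Ablation Rate. The change should be made because the fault is certain and the repair is simple.

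**What to change.** In SAP 8.10.3 and 8.10.4, use Clopper-Pearson (or Wilson) for the crude proportions whatever the observed value, in line with SAP 8.15. Add a sentence to 8.10.4 that with no LTP events the exact interval is the one reported, because the log-log Kaplan-Meier interval is then undefined. Using the same wording in 8.10.1 and 8.10.2 is optional, for consistency.

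The cost is SAP wording only, with no new data and no effect on sample size. Some intervals become slightly wider.

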In terms of the clinical results of thermal ablation therapy for primary lung cancers, two large multicenter, prospective and observational studies in patients with stage IA NSCLC found that the results of thermal ablation in clinically inoperable patients are similar to the results reported in previous stereotactic radiotherapy, the OS of thermal ablation therapy was ~86% in 1 year and ~69% in 2 years^{15,16}. Two large national cancer database studies found no significant difference in OS between thermal ablation and stereotactic radiotherapy for early NSCLC^{17,18}. In advanced NSCLC, thermal ablation is proven to be an effective treatment for local recurrence after radiotherapy.

Therefore, thermal ablation is considered as a palliative treatment option for advanced NSCLC^{12,19}.

There are increasingly more literatures on the clinical results of thermal ablation for the treatment of secondary lung cancers, especially lung metastasis from colorectal cancer, but it is mainly based on observational studies. A large systematic review included 8 observational studies involving a total of 903 patients with colorectal cancer lung metastases. The 1-year, 3-year, and 5-year survival was 89%, 44%, and 19.9%, respectively, while the tumor-free survival was 60.5%, 14.4% and 7% respectively²⁰. Another prospective observational study found that, for small secondary lung cancer, repeated thermal ablation can achieve similar survival benefits as surgical resection. This study included 566 patients with a total of 1037 secondary lung cancers, through repeated thermal ablation therapy and control of lung cancers in this population during the follow-up period, the median OS was 62 months, the 5-year survival was 51.5%, and the 4-year local treatment efficacy was 89%²¹.

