- Progression at other site to be evaluated by a study physician or may be reported by a patient's primary treating oncologist. If there is a progression, the study physician should specify if the progression is a new lung malignant tumor, or a distant metastasis.
- Any unplanned hospitalization in any hospital for any reason within 30 days post-ablation will be recorded, and the investigator will assess the reason for re-admission and record it in the study database.
- Relevant concomitant medication: including blood thinning/anticoagulants, antineoplastic agents such as chemotherapy/ targeted therapy/ immunotherapy, steroids, anti-inflammatories, NSAIDs, antibiotics and medications used to treat relevant medical history and adverse events.
- Concomitant procedure: the name, time, site and purpose of the concomitant procedure (including but not limited to puncture, radiotherapy, ablation therapy and surgical resection).
- All AEs and SAEs.

Note: Within the study, re-ablations on the initially ablated target tumor(s) should not be performed before the Visit 3 assessment for Technical Efficacy has been completed. If investigators assess it is medically indicated/necessary to re-ablate before the Visit 3 Technical Efficacy assessment, the re-ablated tumor's Technical Efficacy assessment will be counted as failure. The re-ablation will not change or extend the subject's follow-up schedule.

4) Visit 4 to visit 6 (end of study)

Visit 4 will occur at 3 months (\pm 14 days), Visit 5 will occur at 6 months (\pm 1 month), and Visit 6 will occur at 12 months (\pm 1 month) after surgery during which subjects will return to the study site for the following assessments:

- ECOG performance status score.
- Quality of Life questionnaire: the QOL questionnaires include the EORTC QLQ-C30 and the lung-specific QLQ-LC13 (Visits 5 and 6 only).
- Enhanced CT scan of the lung.
- Document the investigator's determination of Local Tumor Progression.

- Submit the CT images to the IRC for determination of whether Local Tumor Progression has occurred or not.
- Progression at other site to be evaluated by a study physician or may be reported by a patient's primary treating oncologist. If there is a progression, the study physician should specify if the progression is a new lung malignant tumor, or a distant metastasis.

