existing literature, and then the point estimate and corresponding 95% confidence interval were estimated by meta-analysis using random effects. The meta-analysis results showed that, prior studies based on a variety of populations have a mean Technical Efficacy rate of 87% (95%CI: 79%-92%) after MWA of lung cancer at 1 month. Considering that PG is the minimum threshold of the acceptable performance, new product-related study curve, clinically significant Technical Efficacy rate, and lower limit of the above 95% confidence interval, the PG of the study is set as 80%. The primary analysis of Technical Efficacy will be performed at the Target Tumor level and at the subject level on the Full Analysis Set. For multi-target-tumor subjects, the largest Target Tumor, determined by the maximum three dimensions of each target tumor, will be used for the subject-level analysis. This will be repeated for the Per Protocol Set.

An additional analysis will be conducted based on the investigators evaluation of Technical Efficacy Rate.

- **Secondary endpoints:**

1. The number and percentage of tumors with Technical Success Rate, A0 Ablation Rate, and Re-ablation Technical Success Rate will be summarized and 95% confidence interval will be estimated based on the Normal Approximation to the Binomial distribution.
 - Technical Success Rate and A0 Ablation Rate will be based on ablation zone tumor coverage and the ablation margin achieved after the first ablation and prior to any repeat ablations.
 - Re-Ablation Technical Success Rate will be based on ablation zone tumor coverage and ablation margin achieved after re-ablation.
2. Local Tumor Progression will be estimated using Kaplan-Meier method and 95% confidence interval will be provided.
3. Progression-Free Survival and Overall Survival will be estimated based on patient level using Kaplan-Meier method and 95% confidence interval will be provided.
4. The summary description of pain scores, ECOG scores and Quality of Life scores will be reported based on patient level according to the standard recommended method.
5. The length of stay as well as the number and percentage of readmissions will be described based on the patient level, and the reasons for readmission will be counted and percentage will be calculated.
6. Ablation Procedure Related Indicators will be reported descriptively.

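### The planned Kaplan-Meier rates for Local Tumor Progression (LTP) describe progression in the absence of death; a cumulative incidence with death as a competing event should be added beside them

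*SAP*

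**What the plan says.** Protocol 8.1, under secondary endpoints, gives one sentence on the method: "Local Tumor Progression will be estimated using Kaplan-Meier method and 95% confidence interval will be provided". SAP 8.10.4 supplies the detail, at the level of the target tumor:

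- **Rates over time.** "Local tumor progression rates of any original-ablated tumor(s) at 3, 6, 9, and 12 months will be estimated by the Kaplan-Meier method", with Greenwood variance and a log-log interval.
- **Event date.** The time to LTP is "determined by the CT imaging date, including unscheduled visits".
- **Censoring.** "For original-ablated tumor(s) without LTP during the study follow-up period, the tumors will be censored at the date of last local tumor assessment". No exception is made for death. The frequency of censoring reasons is to be reported, but the reasons are not listed.
- **Crude summary.** The same section also plans that "The number and proportion of target tumors with local tumor progression will be summarized", with a 95% CI.

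The neighbouring section on progression-free survival (SAP 8.10.5) restricts censoring to subjects who are alive and free of progression. SAP 8.14 refers back to 8.10.4 to 8.10.6 for censored data. Neither document names a competing-risk method. SAP 8.10 states that secondary endpoints are not tested.

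**The concern.** An ablated tumor cannot progress locally once the subject has died, so death without LTP is a competing event. Kaplan-Meier with such tumors censored treats them as if they could still have progressed later, at the same rate as tumors still under observation. The result is the LTP risk in a hypothetical setting without death, and only if death and LTP are independent. It is not the share of ablated tumors that progress locally in this population.

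Many readers of a 12-month LTP rate will take it as that share. Deaths within the year are plausible: for stage IA NSCLC the protocol cites that "the OS of thermal ablation therapy was ~86% in 1 year", and for colorectal lung metastases it cites 89%. At stake is the meaning of a reported secondary rate and its interval, not the success criterion.

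**Working it through.** **Inputs from the documents.** 1-year survival of about 86% (NSCLC) and 89% (colorectal lung metastases), both in Protocol 4.1.2, which means 14% and 11% deaths. Protocol 4.2 cites a series, mostly treated with this device, with a median survival of 58.6 months. With a constant hazard that gives 1 − 0.5^(12/58.6) = 13% deaths at 12 months, in line with the other two.

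**Assumptions.** The documents give no 12-month LTP rate and no mortality assumption for this trial, so there is no planned LTP figure to reproduce. I take LTP (one minus Kaplan-Meier) of 5% to 20%, constant and independent hazards, and 2% to 5% deaths as a low-mortality range.

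**Formula.** With a = −ln(1 − LTP) and b = −ln(1 − deaths), the 12-month cumulative incidence is

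CIF = a/(a + b) × [1 − exp(−(a + b))].

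**Example, LTP 10% and deaths 14%.** a = 0.1054 and b = 0.1508. The bracket is 1 − 0.90 × 0.86 = 0.226. CIF = 0.1054/0.2562 × 0.226 = 9.29%. The excess is 10 − 9.29 = 0.71 points, or 0.71/9.29 = 7.6% of the CIF.

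| LTP (1 − KM) | Deaths at 12 months | CIF | Excess, points | Excess relative to CIF |
|---|---|---|---|---|
| 5% | 11% | 4.72% | 0.28 | 5.9% |
| 5% | 14% | 4.64% | 0.36 | 7.7% |
| 10% | 2% (assumed) | 9.90% | 0.10 | 1.0% |
| 10% | 5% (assumed) | 9.75% | 0.25 | 2.5% |
| 10% | 11% | 9.45% | 0.55 | 5.8% |
| 10% | 14% | 9.29% | 0.71 | 7.6% |
| 20% | 11% | 18.92% | 1.08 | 5.7% |
| 20% | 14% | 18.62% | 1.38 | 7.4% |

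**Check with the visit schedule.** I simulated 400,000 tumors per scenario, with CTs exactly at 1, 3, 6 and 12 months and censoring at the last CT. At LTP 10%, Kaplan-Meier gives 9.99% against Aalen-Johansen 9.25% (11% deaths), and 10.0% against 9.06% (14% deaths). The gap of 0.7 to 0.9 points is a little wider than in the closed form because LTP is seen only at visits, so LTP arising between the last CT and death goes unseen.

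**Scale.** At LTP 10% the approximate 95% half-width is 1.96 × √(0.10 × 0.90/n), which is 5.4 points for 120 tumors and 4.4 for 180. The tumor counts are assumed, and the formula ignores censoring and the clustering of tumors within subjects.

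**Crude proportion.** With nobody lost and CTs on schedule it equals Aalen-Johansen (9.25% and 9.06%). With visits spread over their windows and 11% deaths it is 9.16% with no loss, and 8.67% with an assumed 10% lost to follow-up.

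**The case against.** **Kaplan-Meier is a legitimate choice of estimand.** LTP is a tumor-level measure of local control, and the plan never says that the Kaplan-Meier value is the share of all ablated tumors that progress. This stands. It is a reason to keep the curve and to label it, not to leave it as the only time-specific rate.

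**The crude proportion already keeps deaths in the denominator.** This is partly right, and it means the reader is not left with Kaplan-Meier alone. But that proportion is not tied to 3, 6, 9 or 12 months. It counts tumors lost to follow-up as free of LTP, or drops them if the rule on missing data in SAP 8.1 is applied to them. Protocol 10.2 expects some loss. It therefore does not replace a cumulative incidence.

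**The mortality figures are borrowed.** This also stands. They come from literature populations. The trial also admits patients who decline surgery, limits NSCLC to stages IA1-IA2 and tumors to 2 cm, and excludes uncontrolled primary lesions and an expected survival below 6 months. Lower mortality is possible, hence the 2% to 5% rows.

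**A reader might infer that the reported 12-month rate always overstates true local progression.** The documents do not support that. Events are dated by CT, and although "Visit 6 will occur at 12 months", its window runs a month past that. If Visit 6 CTs are spread evenly over the window (an assumption), about half fall after month 12. At LTP 10% and 11% deaths, Kaplan-Meier at month 12 is then 8.27%, below a true incidence of about 9.4%, though still above Aalen-Johansen on the same data (7.59%). The upward direction is assured only against the cumulative incidence on the same data. The window effect is a separate matter that lowers both estimators.

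**Conclusion.** The point holds in a limited form. As written, the censoring rule makes one minus Kaplan-Meier an estimate of LTP in the absence of death. On the same data it cannot fall below the cumulative incidence with death as a competing event. At the mortality cited in the protocol the 12-month excess is about 0.55 to 0.71 points at LTP 10% and 1.1 to 1.4 points at 20%, which is about 6% to 8% of the cumulative incidence. At 2% to 5% mortality and LTP 10% it is 0.10 to 0.25 points. These figures rest on constant, independent hazards and on assumed LTP rates.

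The excess lies well within the confidence interval. LTP is not tested, and success and submission rest on the Technical Efficacy Rate, so it would be wrong to infer that any trial decision is affected. This is a cheap improvement to the meaning of a reported rate.

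**What to change.** In SAP 8.10.4:

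1. Add the Aalen-Johansen cumulative incidence of LTP at 3, 6, 9 and 12 months, with death without LTP as the competing event and a 95% CI at each time point.
2. Keep the Kaplan-Meier estimate as a supplement, labelled as LTP in the absence of death, for comparison with published Kaplan-Meier rates.
3. Report death separately among the censoring reasons of the Kaplan-Meier analysis.

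The cost is SAP wording and a small programming change in SAS. Death dates are already collected for overall survival, so no new data are needed. The one downside is that two time-specific LTP estimates appear in the report and must be clearly labelled.
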